Important questions remain in order to validate the efficacy and potential cost-effectiveness of ESTEEM. Accordingly, we propose a 3-arm RCT that would examine (1) whether ESTEEM (arm 1) demonstrates significant improvements compared to existing LGBT-affirmative community mental health treatment (CMHT; arm 2) or standard HIV/STD voluntary counseling and testing (VCT; arm 3) for high-risk depressed and anxious YGBM and (2) whether it improves outcomes through reducing hypothesized cognitive, affective, and behavioral minority stress processes. A transdiagnostic treatment like ESTEEM capable of simultaneously improving mental, behavioral, and sexual outcomes in a relatively short amount of time maximizes treatment resources in constrained economic contexts because it reduces the need for training in multiple interventions for multiple problems. Yet, as the field has been re-examining the potential utility of individual interventions to affect the HIV epidemic, ESTEEM's potential cost-effectiveness in terms of averted mental disorders and HIV infections represents an essential public health question. These unanswered questions will be addressed:

**Aim 1: Test the efficacy of ESTEEM against (1) community mental health treatment (CMHT) and (2) HIV/STD voluntary counseling and testing (VCT).** Our primary outcome is condomless anal sex in the absence of PrEP, with any HIV+ partner (except primary partners with a known undetectable viral load), casual partner, or status-unknown partner. Knowing whether ESTEEM yields greater improvement than time-matched CMHT will establish the benefit of our *transdiagnostic* approach. Comparing ESTEEM to VCT offers a strong test of ESTEEM's incremental cost-effectiveness.

**Aim 2: Determine whether ESTEEM works through its hypothesized cognitive, affective, and behavioral minority stress processes.** 4-, 8-, and 12-month follow-ups will determine if improvements in minority stress processes precede and statistically mediate outcome

improvements. Mediation will validate the minority stress theory of ESTEEM and provide transdiagnostic targets for future YGBM health interventions.

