**Confidentiality & Security of Data:**

1. What participant information will you be collecting?

The full packet of study measures and assessments is attached to this application. We propose to collect information about participants' general mental health status; HIV risk; demographics; HIV status; chlamydia and gonorrhea infection; experiences with stigma-related stress; depression and anxiety; cognitive, affective, and interpersonal functioning (e.g., rumination, social support, impulsivity, assertiveness); mental health treatment history and perspectives; substance use; sexual compulsivity; and perceptions of intervention helpfulness. We will also video tape-record all intervention sessions. Counselors will also complete session notes. Each participant will have a binder that contains all session notes. No name will be attached to the binder, only participant ID. The binders will be locked in a filing cabinet.

Participants will provide the following data at baseline and 4-, 8-, and 12-month follow-up appointments: (1) quantitative assessments, previously used with young gay and bisexual men, of mental health, substance use, and stigma-related stress, (2) interviewer-administered timeline follow-back of HIV risk behavior, including condomless anal, sex while under the influence of drugs or alcohol, PrEP use and adherence, and number of sexual partners, during the previous 3 months, (3) interviewer-administered mental health assessment with the Mini-International Neuropsychiatric Interview (MINI), (4) OraSure rapid HIV 1/2 antibody test (at baseline and 12-month follow-up), (5) urine sample and rectal and oral swabs for chlamydia and gonorrhea testing (at baseline and 12-month follow-up), and (6) engagement in the intervention.

Participants who complete remote assessments will be asked to provide their address to research staff to aide in establishing contact with the nearest emergencies services, if necessary. This information will be stored in a password protected contact database on secure Box only accessible to research staff. Once addresses are stored in the database, any emails containing identifiable participant information will immediately be hard deleted from study inboxes.

2. Will any of the following identifiers be collected?

- Names
- All geographic subdivisions smaller than a State, including: street address, city, county, precinct, zip codes
- Telephone numbers
- Fax numbers
- E-mail addresses
- Social Security numbers

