Main Inclusion Criteria	(1) aged 18–35, (2) identify as a gay or bisexual man, (3) HIV-negative status confirmed through in-office testing, (4) diagnosis of any Diagnostic and Statistical Manual (DSM-5) depressive, anxiety, or trauma- and stressor-related disorder; (5) HIV sexual risk (≥ 1 act in past-90-day of condomless anal sex with a male partner of unknown status or HIV+ status, unless with a HIV+ primary/main partner with known undetectable viral load); (6) not currently adherent to PrEP (pre-exposure prophylaxis) (defined as taking 4 or more days per week) (7) NYC or Miami residential stability and planned availability for 12 months; and (8) provision of informed consent.

STATISTICAL ANALYSIS PLAN

Intervention	ESTEEM is a 10-session intervention based on the Unified Protocol, an individually-delivered cognitive behavioral therapy (CBT) intervention with efficacy for reducing stress-sensitive mental health disorders (e.g., depression, anxiety) by enhancing emotion regulation skills; reducing avoidance patterns; and improving motivation and self-efficacy for behavior change. The Unified Protocol employs modules for motivation enhancement, interoceptive and situational exposure, cognitive restructuring, mindfulness, and self-monitoring techniques. Through an extensive adaptation process, we adapted the Unified Protocol to enhance young gay and bisexual men’s stigma coping by reducing minority stress processes.
Duration of Intervention	10 therapy sessions in 4 months.
Primary Outcome	The primary outcome is condomless anal sex in the absence of either PrEP or known undetectable viral load of HIV+ primary partners, measured with the Time-Line Follow-Back (TLFB), a semi-structured interview. The TLFB yields past-90-day incidence of HIV risk behavior: condomless anal sex, sex while using drugs or alcohol, number of sexual partners, and preceding-week PrEP use (i.e., coverage defined as 4+ doses per week). TLFB interviewers are masked to study arm. The primary outcome is assessed at 8-month follow-up.

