8.2 Comparability of Treatment Groups

To determine randomization effectiveness, differences in baseline demographic characteristics will be assessed between ESTEEM, CMHT, and VCT-only groups using appropriate graphical and statistical methods including summary statistics. The randomization is designed to produce balance on important covariates. If we find imbalance on key covariates, we will consider sensitivity analyses that adjust for those covariates. Study site will be included as a covariate in all analyses because randomization was stratified by study site.

STATISTICAL ANALYSIS PLAN

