8.3.2 Supportive Analysis of the Primary Outcome: Number of Condomless Anal Sex Acts

STATISTICAL ANALYSIS PLAN

Analysis	Supportive analysis of primary outcome: number of condomless anal sex acts in the absence of either PrEP or known undetectable viral load of HIV+ primary partners, measured with the TLFB, a semi-structured interview.
Analysis population	All enrolled participants
Endpoint	8-month as reported on TLFB
Unit of analysis	Participant
Method of analysis*	Generalized linear mixed model with a log link (Poisson model) using a contrast to test the comparison at the primary time point of 8 months adjusting for site and baseline number of sex acts. We will conduct the comparison of ESTEEM versus VCT at 0.05 level; only if this test is statistically significant will we test ESTEEM versus CMHT at 0.05.
Handling of missing data	MAR assumption
Adjustment covariates	A priori covariates include: study site (NYC or Miami); baseline number of sex acts
Type I error	5% (2-sided)
Control of type I error	We will use a gatekeeping strategy. If the first comparison is significant at 0.05, then we will conduct the second comparison at 0.05.
Treatment effect estimate	Risk ratio with 95% confidence limits

*We will assess for overdispersion. If there is a large amount of overdispersion, we will correct the Poisson model to take this into account. We will also assess for zero-inflation. If there are excess zeros, we will use a zero-inflated Poisson model.

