8.4.2.1 Continuous Measures

Analysis	Mental Health and Substance Use: depression severity; anxiety; drug abuse; alcohol abuse; suicidality
Analysis population	All participants
Endpoint	Scale values at 8 and 12 months of follow-up
Unit of analysis	Participant
Method of analysis	Linear mixed model assuming missing at random (MAR)
Handling of missing data	MAR assumption
Adjustment covariates	A priori covariates include: study site (NYC or Miami); baseline score
Type I error	5% (2-sided)
Control of type I error	To control the false discovery rate, we will use the Benjamini and

STATISTICAL ANALYSIS PLAN

	Hochberg (1988) method.
Treatment effect estimate	Marginal least square mean (LSM) with 95% confidence limits if there is no treatment by time interaction ($p < 0.10$); otherwise, LSM will be summarized for each treatment and timepoint.

Sensitivity analyses will be conducted to investigate the MAR assumption, such as methods that model jointly the missingness and outcome distributions (National Research Council, 2010).

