8.4.3 Minority Stress- Mediation analysis

We plan to model minority stress mediators (rejection sensitivity, internalized homophobia, sexual orientation concealment) as a latent variable at the 4- and 8-month time points. We will then use these constructs in latent variable mediation models using structural equation modeling to examine whether 4-month minority stress mediates 8-month sexual risk and mental health outcomes; and whether 8-month minority stress mediates 12-month sexual risk and mental health outcomes. The mediation models will include test of exposure-mediation interactions (Valeri and VanderWeele 2013; Muthan and Asparoutov 2015), to consider potential confounding of the mediation-outcome relationship and allow for causal interpretation. In case of support for a mediating effect of minority stress in the above latent variable mediation model, we will apply a sequential approach in our analyses of mediation to estimate both the joint effect through all mediations, as well as, give consideration to how much of the combined effect is attributed to each mediator (Vansteelandt and Daniel 2017; VanderWeele and Vansteelandt 2014).

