8.5.2 Mental health mediators

We will follow a similar analysis plan as proposed in 8.4.3 and 8.4.4 using the mental health variables as the mediators and determining the mediating relationship on HIV risk outcomes using both latent variable mediation models and mediation analysis with multiple mediators.

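### The mediation models in SAP 8.4.3, 8.4.4 and 8.5.2 rely on an arm-by-mediator interaction test to deal with mediator-outcome confounding, and adjust for nothing but site

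*SAP*

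**What the plan says.** SAP 8.4.3 models minority stress as a latent variable at 4 and 8 months. It asks whether the 4-month value mediates 8-month outcomes and whether the 8-month value mediates 12-month outcomes. The models include an exposure-mediator interaction test, whose stated purpose is "to consider potential confounding of the mediation-outcome relationship and allow for causal interpretation". Section 8.4.4 repeats that purpose word for word for the universal mediators. Section 8.5.2 says: "We will follow a similar analysis plan as proposed in 8.4.3 and 8.4.4 using the mental health variables as the mediators".

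None of the three sections lists covariates. The one adjustment that reaches them is the general statement in 8.2: "Study site will be included as a covariate in all analyses because randomization was stratified by study site". Baseline adjustment appears only for other models:

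- 8.4.2.1, continuous mental health and substance use scores: "A priori covariates include: study site (NYC or Miami); baseline score".
- 8.3.2, count of acts: "A priori covariates include: study site (NYC or Miami); baseline number of sex acts".

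The Protocol's Statement of Purpose (Aim 2) sets the weight placed on the result: "Mediation will validate the minority stress theory of ESTEEM and provide transdiagnostic targets for future YGBM health interventions".

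**The concern.** Arm is randomised and the mediators are not. The arm-to-mediator path is therefore protected, but the mediator-to-outcome path is an observational association. A stable disposition, such as general distress, could raise both minority stress at 4 months and symptoms or sexual risk at 8 months. Mediator and outcome would then be associated within each arm even if changing the mediator did nothing.

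The interaction test looks for a difference between the arms in the mediator-outcome slope. A common cause that acts alike in both arms shifts both slopes equally, so the test cannot see it, and fitting the interaction term does not remove it. Measuring the mediator one visit before the outcome limits reverse causation but leaves common causes in place.

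At stake is the reading of Aim 2 and of the tertiary mediation analysis. A treatment effect on stress plus a pre-existing correlation between stress and outcome could be reported as support for the theory behind the intervention.

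**Working it through.** The documents give no power or effect size for mediation, so there is no planned figure to reproduce. The check asks two things: how large the false indirect effect can be, and whether the interaction test reacts to it.

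**Inputs from the SAP.** Section 6.2 gives 80, 80 and 40 evaluable participants, and 100/100/50 randomised at 80% retention (80/0.8 = 100; 40/0.8 = 50).

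**Assumed inputs.** Mediator and outcome, at baseline and follow-up, each equal √s × trait + noise, with unit variance. Stability s is 0.6 or 0.8. The two traits correlate at ρ = 0.1, 0.3, 0.5 or 0.7. The arm effect d on the follow-up mediator is 0.1, 0.25 or 0.5 SD. The true mediator effect on the outcome is zero. One observed mediator stands in for the latent variable. False mediation means that the arm-to-mediator path and the mediator-to-outcome path are both significant at 0.05.

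**Spurious indirect effect.** Write c = ρs.

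- Without baselines the mediator-outcome slope is c, so the false indirect effect is d × c. At d = 0.5 and ρ = 0.3-0.7 it runs from 0.5 × 0.3 × 0.6 = 0.09 SD to 0.5 × 0.7 × 0.8 = 0.28 SD.
- With baseline mediator and baseline outcome the slope becomes c(1 − s)/(1 + s − 2c²). The smallest case (ρ = 0.3, s = 0.8) is 0.24 × 0.2/(1.8 − 0.1152) = 0.028, which gives 0.01 SD. The largest (ρ = 0.7, s = 0.6) is 0.42 × 0.4/(1.6 − 0.3528) = 0.135, which gives 0.07 SD.

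**Hand check of one row (80 vs 80, d = 0.5).** The arm path has noncentrality 0.5 × √(80 × 80/160) = 3.16 and power 0.88. Without baselines the mediator path at c = 0.18 has noncentrality 0.18/√(1 − 0.18²) × √157 = 2.29 and power 0.625; at c = 0.56 its power is about 1. The products are 0.55 and 0.88. With baselines the products at the two extreme cases are 1.00 × 0.064 = 0.06 and 0.98 × 0.39 = 0.38.

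**Simulated false mediation, ρ = 0.3-0.7**, at arm effects 0.5 / 0.25 / 0.1 SD:

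| Contrast, outcome | Without baselines | With baselines |
|---|---|---|
| vs CMHT (80/80), continuous | 56-89% / 22-36% / 6-11% | 6-38% / 4-21% / 1-5% |
| vs VCT-only (80/40), continuous | 37-73% / 12-25% / 4-9% | 5-27% / 3-11% / 1-3% |
| vs CMHT (80/80), binary | 34-89% / 13-35% / 3-10% | 8-34% / 4-19% / 1-5% |
| vs VCT-only (80/40), binary | 24-74% / 6-24% / 3-9% | 7-23% / 3-12% / 1-3% |

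Continuous cells use 3,000 trials and linear regression; binary cells use 2,000 trials and logistic regression. The binary rows take 8-month risks of 40%, 80% and 85%, which are the SAP's 60%, 20% and 15% reductions from an assumed baseline risk of 1. They adjust for a baseline act count of at least 1 with an assumed median of 4.

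At ρ = 0.1 (continuous, 80/80, no baselines) the rates are 10-15% / 4-7% / 1-2%.

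**Does the interaction test warn?** It rejected in 4.3-5.4% of continuous trials and 1.9-5.6% of binary trials.

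**Second model.** Here one baseline common cause loads g on both mediator and outcome, the arm effect is −0.5 SD, the true mediator effect is zero, and there are 80 per arm. The false indirect effect should be −0.5g². Simulated means with site only, then with the interaction term added, were −0.045 and −0.044 (g = 0.3), −0.128 and −0.127 (g = 0.5), and −0.248 and −0.247 (g = 0.7). The term changes almost nothing. With no confounding and a real interaction (main slope 0.3, interaction 0.4), the test rejected in 68% of runs. It responds to effect modification, not to confounding.

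**The case against.** **The wording is soft.** The SAP says the test is there to consider confounding, which is weaker than claiming to remove it, and the phrase may loosely describe the causal-mediation methods cited beside it. But the same sentence claims causal interpretation, and a citation does not pre-specify a covariate set. The SAP names a priori covariates for other outcomes and none here.

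**The aims imply a baseline reference.** SAP Section 2 speaks of improvements in stress processes and omits the Protocol sentence about validating the theory. That does not put a baseline value in the model, but it does mean the columns without baselines show one reading of a silent text.

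**The percentages rest on assumptions.** This stands. Arm effect, trait correlation, stability and a zero true effect are all assumed. A single observed mediator replaces the latent variable, and the SAP does not name the joint-significance test. At ρ = 0.1 and an arm effect of 0.25 SD or less, the continuous 80/80 rate without baselines is only 1-7%. The figures show what can happen, not what will happen in this trial.

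**Baseline adjustment is not a cure.** This also stands. Up to 38% remains in the worst adjusted cell. In the second model, adjusting for the true common cause restores 4-5%, but the trial does not observe that variable, so the figure must not be read as the result of the proposed change.

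**Conclusion.** The concern holds. The purpose given to the interaction test is wrong as written, whatever the sizes turn out to be, and nothing specified beyond site addresses mediator-outcome confounding. The risk is large if ESTEEM moves the mediator by about 0.5 SD and the traits correlate at 0.3 or more. It is small if either quantity is small. Confidence is high on the logic and on the missing covariates; the percentages are illustrative. The point affects Aim 2 and section 8.5.2 and should be corrected before those analyses are run. It does not touch the primary comparison.

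**What to change.** In 8.4.3, 8.4.4 and 8.5.2:

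1. Put the pre-randomisation mediator, the baseline outcome and site in both the mediator and the outcome equations. For symptoms use the baseline score. For sexual risk use the baseline number of acts: entry requires at least one "act in past-90-day of condomless anal sex with a male partner of unknown status or HIV+ status" (Study Summary, Main Inclusion Criteria), so a yes/no baseline would barely vary.
2. Keep the interaction term for effect decomposition only, and delete the statement that it deals with confounding.
3. State the assumption of no unmeasured mediator-outcome confounding.
4. Because residual bias remains, add a sensitivity analysis that varies the residual mediator-outcome correlation and reports the value at which the indirect effect disappears.

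Two side points carry no weight in the conclusion. The mediation sections should name the contrast (vs CMHT, vs VCT-only, or both). In 8.4.4 the condition that triggers the decomposition names minority stress where it should name the universal mediators.

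The cost is SAP wording, a few covariates, slightly larger models and one sensitivity analysis. Protocol Section VI says "Participants will provide the following data at baseline and 4-, 8-, and 12-month follow-up appointments", and the list covers mental health, substance use, stigma-related stress and the timeline follow-back. It does not name the computerised tasks (IAT, Go/No-Go, SRET), so confirm that these have baseline values.

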8.4.4 Universal Mediators- Mediation analysis

We plan to model universal mediators (DERS, RRS, RAS, MSPSS, cognitive bias, impulsivity) as a latent variable at the 4- and 8-month time points. We will then use these constructs in latent variable mediation models using structural equation modeling to examine whether 4-month universal mediators mediate 8-month sexual risk and mental health outcomes; and whether 8-month universal mediators mediates 12-month sexual risk and mental health outcomes. The mediation models will include test of exposure-mediation interactions (Valeri and VanderWeele 2013; Muthan and Asparoutov 2015) to consider potential confounding of the mediation-outcome relationship and allow for causal interpretation. In case of support for a mediating effect of minority stress in the above latent variable mediation model, we will apply a sequential approach in our analyses of mediation to estimate both the joint effect through all mediations, as well as, give consideration to how much of the combined effect is attributed to each mediator (Vansteelandt and Daniel 2017; VanderWeele and Vansteelandt 2014).

STATISTICAL ANALYSIS PLAN

Mediation analysis

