4.2 Secondary Outcomes

Condomless anal sex at 12 months (binary); Condomless anal sex at 8 and 12 months (count); Depression severity, as measured using the HAMD depression severity score, ODSIS, and BSI at 8 and 12 month time points; Anxiety, as measured by the BAI, OASIS, BSI, and SIAS at 8 and 12 month time points; Drug abuse, as measured by the SIP-D at 8 and 12 month time points; Alcohol abuse, as measured using by the AUDIT at 8 and 12 month time points; Mental health, as defined by odds of no longer having at least one *DSM-5* diagnosis (e.g., depression, anxiety) that was present at baseline still be present at 8 and 12 month time points based on the MINI (binary); Suicidality as measured by SIDAS at 8 and 12 month time points (continuous); Minority stress as captured by rejection sensitivity measured using RS, internalized homophobia measured using IHS and IAT; and sexual orientation concealment measured using SOCS at 4 and 8 month time points (continuous); Universal stress processes as captured by emotional regulation as measured by DERS, rumination as defined by RRS, assertiveness as measured by RAS, social support as measured by MSPSS, cognitive bias as measured by SRET, and impulsivity measured by Go/No-Go at 4 and 8 month time points (continuous).

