6.2 Sample Size Determination for the Primary Outcome

Sample size calculations were carried out using PASS 12 for logistic regression.

Our primary goal is to demonstrate a greater reduction at 8 months in condomless anal sex in the absence of either PrEP or known undetectable viral load of HIV+ primary partners, in the ESTEEM arm versus the CMHT and VCT-only arms. In our pilot study, we saw a 60% reduction in condomless anal sex at 6 months in the ESTEEM arm. We used these estimates to inform our 8-month endpoint.

Based on previous studies of VCT and the fact that CMHT does not specifically focus on condomless anal sex, we expect that these arms will yield lower reductions compared to ESTEEM, but a slightly larger reduction in CMHT (20%) compared to VCT-only (15%). To achieve at least 90% power at a 5% type I error rate, accounting for an R-square of 0.1 between treatment arm and the covariates (e.g., site, race/ethnicity), we will need 80 individuals in the ESTEEM and CMHT arms, and 40 individuals in the VCT-only arm. Although we plan to take steps to increase our retention rate from our pilot study, we conservatively estimate the retention at 8 months to be 80%. Therefore, we planned to randomize 100 ESTEEM, 100 CMHT, and 50 VCT-only young gay and bisexual men. The original target sample size was 250 participants enrolled from the two study sites [New York: 150 (60 ESTEEM, 60 CMHT, 30 VCT) and Miami: 100 (40 ESTEEM, 40 CMHT, 20 VCT)]. This was increased to 254 on 2/28/18 to correct an imbalance in the 2:2:1 randomization. The final sample size was 254.

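### SAP 8.4.4 ties the mediator-by-mediator analysis of the universal processes to the minority-stress result, probably through a carried-over sentence; the trigger must name the universal-mediator model

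*SAP*

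**What the plan says.** SAP 8.4.3 covers minority stress: "We plan to model minority stress mediators (rejection sensitivity, internalized homophobia, sexual orientation concealment) as a latent variable". The count is three constructs, or four measures if both instruments in SAP 4.2 enter ("internalized homophobia measured using IHS and IAT").

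SAP 8.4.4 covers a separate set: "We plan to model universal mediators (DERS, RRS, RAS, MSPSS, cognitive bias, impulsivity) as a latent variable".

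Both sections then use the same conditional sentence: "In case of support for a mediating effect of minority stress in the above latent variable mediation model, we will apply a sequential approach". The step it unlocks estimates the joint effect through all mediators and will "give consideration to how much of the combined effect is attributed to each mediator".

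SAP 8.5.2, on mental-health mediators, says "We will follow a similar analysis plan as proposed in 8.4.3 and 8.4.4", names both the latent-variable and the multiple-mediator analysis, and restates no condition.

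Neither 8.4.3 nor 8.4.4 says what counts as support: no test, significance level, outcome, pair of time points or comparator arm. No power is given for mediation.

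**The concern.** Aim 2 asks whether ESTEEM works through its cognitive, affective and behavioral processes, and the protocol says mediation will provide targets for later interventions. Which process carries the effect is therefore part of the answer, and the conditional step is where the plan gives it.

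In 8.4.3 the condition names that section's own construct. In 8.4.4 it names the other section's construct. This is an operative decision rule, so two analysts following the text could run different analyses and both claim to have followed the plan.

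**Working it through.** **1. Literal and corrected trigger compared for the universal processes.**

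| Universal model supported | Minority-stress model supported | Decomposed, literal 8.4.4 | Decomposed, trigger on universal model |
|---|---|---|---|
| yes | yes | yes | yes |
| yes | no | **no** | **yes** |
| no | yes | **yes** | **no** |
| no | no | no | no |

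The rules disagree in two of four cases. This needs no numerical assumption.

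**2. Is there another route to the individual processes?** SAP 8.4 promises that each secondary outcome is analysed separately as set out below it. The linear mixed model in 8.4.2.1 lists only depression, anxiety, drug abuse, alcohol abuse and suicidality. For the stress processes only 8.4.3 and 8.4.4 follow. No unconditional method for an individual stress process is described.

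**3. The plan's nearest power figure.** SAP 6.3 states 80% power at alpha 0.01 for 0.55 (vs CMHT) and 0.70 (vs VCT-only). The evaluable numbers come from SAP 6.2: "we will need 80 individuals in the ESTEEM and CMHT arms, and 40 individuals in the VCT-only arm". Power = Φ(d·√(n1·n2/(n1+n2)) − 2.576), two-sided.
- 0.55, 80 vs 80: 0.55 × √40 = 3.479; Φ(0.903) = 81.7%. This reproduces the stated 80%.
- 0.70, 80 vs 40: 0.70 × √26.67 = 3.615; Φ(1.039) = 85.1%. This is somewhat above the stated 80%.

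I use 0.55 and 80 vs 80 below as the assumed shift in a mediator. The documents give no treatment effect on the mediators.

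**4. One process tested alone, treatment-to-mediator path.** Φ(3.479 − z):
- alpha 0.05 (z = 1.960): 93.6%
- alpha 0.05/3 (z = 2.394): 86.1%
- alpha 0.05/6 (z = 2.638): 80.0%

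**5. The pooled test when one process moves by 0.55 SD.** Maximum-likelihood structural models (arm to latent variable to outcome) were fitted to simulated data, 80 vs 80, with 200-300 runs per setting. The Monte Carlo standard error is at most √(0.25/200) = 3.5 points. Assumed, not in the documents: equal indicator correlation of 0.2, 0.3 or 0.5; a continuous outcome; an outcome path of 0.35 from the moved process alone, or 0.40 SD from the average of all; support meaning both paths significant at 0.05.

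| Indicators | Only the moved process drives the outcome | All drive it |
|---|---|---|
| 6 (universal) | 10-32% | 12-17% |
| 4 (minority stress, IHS and IAT separate) | 22-81% | 20-34% |
| 3 (minority stress, constructs) | 48-86% | 32-46% |

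In the same simulations, testing both paths for the moved process alone gave 76-97% unadjusted. With Bonferroni over six it gave 76-81%, for the case where that process alone drives the outcome.

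**6. When all six move by 0.55.** An equal-weight score has standardised effect d/√((1+5ρ)/6). At ρ = 0.5 this is 0.55/0.764 = 0.720, and treatment-path power is 99.5%; at ρ = 0.2 or 0.3 it is about 100%. Any one process tested at 0.05/6 has 80.0% (step 4). The pooled test is then the stronger one.

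**The case against.** **A carried-over sentence, not a decision.** The wording in 8.4.4 matches 8.4.3 exactly, and its reference to the model above points most naturally to the universal model just described, which contains no minority-stress variable. The protocol's Background also uses minority stress processes as an umbrella that includes universal ones. A reader might infer that the team chose to gate the universal analysis on the minority-stress result; the documents do not support that. What stands is that the SAP's own outcome table and section 4.2 treat the two sets as separate domains, so the rule as printed names the wrong one and nothing else in the text resolves it.

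**Latent first is defensible.** The conceptual model has ESTEEM reducing these processes as a set, Aim 2 asks first whether mediation occurs, and pooling wins when all processes move. The documents do not say that only one is expected to move. This stands: the order of analysis is not an error, and step 5 supports an addition rather than a replacement.

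**The power figures are assumption-bound.** This also stands. Sexual risk includes a binary outcome, which was not simulated. The conditional step is mainly estimation, so a detection rate measures it imperfectly, and the power of the multiple-mediator analysis itself was not computed.

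**Section 8.5.2.** It might be read as inheriting the fault. It names both analyses and restates no trigger; its reference to a similar plan leaves some doubt but is not evidence of the defect.

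**Conclusion.** The firm error is the trigger in 8.4.4. As written it gives the wrong instruction whenever the two latent models disagree, and this follows from the text alone. It affects Aim 2 and not the primary outcome.

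The case for also running the individual analysis unconditionally is conditional. For the six-indicator factor, the latent test had about 10-32% power when one process moves by 0.55 SD at 80 vs 80, under the assumptions in step 5. A reader might extend this to both mediator sections. The documents and the calculation do not support that: for three or four minority-stress indicators the range is about 20-86%, because a latent model fitted jointly with the outcome can load on the process that moves.

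Nor can one state how often the literal trigger would block a supported universal analysis. That needs the power of both latent tests and their dependence. The documents give neither, and both models use the same participants and outcomes, so independence is implausible.

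**What to change.** 1. In 8.4.4, make the trigger refer to the universal-mediator latent model of that section. While a trigger remains in 8.4.3 or 8.4.4, state what counts as support: test, level, outcome, time pair and comparator. This costs a few sentences.

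2. As an improvement, run the multiple-mediator analysis in 8.4.3 and 8.4.4 alongside the latent model whatever its result, as 8.5.2 appears to plan for mental-health mediators. Control multiplicity with Benjamini-Hochberg across the individual mediators; 8.4.2.1 already uses false-discovery-rate control. Keep the latent model, which is stronger when the processes move together.

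3. Date the change, and label the added analysis post hoc if any mediation results have already been seen.

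No new data are needed. The downside is more mediation estimates to report: 6 universal plus 3 or 4 minority-stress mediators, so 9 or 10 per outcome, time pair and comparator.
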